4. STUDY DESIGN

This trial is a Phase IV randomized, double-blinded, placebo-controlled study in *Coccidioides* endemic regions in 1000 individuals aged 18 years or older, with community acquired pneumonia (CAP) who meet all eligibility criteria. This study is designed to provide data on the efficacy of early antifungal treatment (fluconazole, 400 mg/day) vs. placebo in subjects with coccidioidomycosis pneumonia. Patients who are prescribed antibacterials by their health care provider for acute CAP will be randomized to receive either placebo or 400 mg/day of fluconazole for 42 days.

Blood work for serologic determination of coccidioidomycosis infection will be drawn at the time of randomization (Day 1), and again on Days 22, 29, and 43. On Day 43, subjects will be informed of their treatment assignment and results of serologic testing from Days 1, 22 and 29. At Day 43, those subjects who did not meet the protocol defined case definition for CAP caused by acute coccidioidomycosis and who did not receive fluconazole will be dismissed from the study and referred to a health care provider with the results of their serology testing and their treatment assignment. All subjects who received fluconazole will be evaluated for safety follow-up at Day 49. At Day 49, those subjects who did not meet the protocol defined case definition for CAP caused by acute coccidioidomycosis be dismissed from the study and referred to a health care provider with the results of their serology testing and their treatment assignment. Subjects who did meet the protocol defined case definition for CAP caused by acute coccidioidomycosis infection will be referred to a healthcare provider with the results of their serology testing and their treatment assignment for further treatment as indicated and will be contacted by telephone on Days 90 and 180. Blood samples will be drawn for safety assessments prior to randomization (Day 1) and again on Days 22, 29 and 43. SAEs, as defined in the protocol, will be collected through Day 49.

The primary clinical outcome will be the proportion of subjects meeting the protocol defined case definition who achieve a clinical response to empiric fungal therapy at Day 22 (based on signs and symptoms of pneumonia via FLEET CAP score).

Secondary outcomes will be measured and include the proportion of subjects with coccidioidomycosis pneumonia who achieve clinical response at Day 43; the mean, median and quartiles for both individual components and composite symptom scores over the evaluable points during the duration of the study period; the time missed from work or school; the SF-12v2; and the numbers of all-cause mortality among subjects with coccidioidomycosis pneumonia.

Exploratory outcomes include: the time to determination of positive serology in both treatment groups; the mean, median and quartiles for individual and composite Extra-Pulmonary Symptom Scores in the absence of disseminated disease; time to onset of dissemination; and the change in FLEET CAP score and its individual components over time among patients with

coccidioidomycosis pneumonia receiving placebo. Further exploratory outcomes include; the safety of empiric fluconazole in this population, specifically with respect to liver function testing; and the adherence to long-term drug administration during this study. Parallel analyses of the primary and secondary outcomes will be performed in subjects satisfying an alternative case definition of coccidioidomycosis pneumonia.

As obtaining samples for future use research has an immense potential value for the scientific community, future use samples will be collected in this study. Please see Section 14.8 for further details.

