Subjects will be informed of their treatment group assignment after all assessments for this visit are completed. Subjects will also be informed of the results of serologic testing from Day 01, Day 22 and Day 29 visits. If the subject meets the protocol defined case definition of CAP caused by acute coccidioidomycosis infection, refer the subject to their identified health care provider.

NOTE: All assessments for this visit must be completed before the subject or study staff performing the assessments are informed of the treatment status. For the remainder of the study, follow-up and additional procedures will be determined based on treatment assignment and whether the subject met the protocol definition of acute coccidioidomycosis pneumonia

Coccidioidomycosis Negative Subjects Who Received Placebo

- Subjects will be provided with all available coccidioidal serology results and their treatment group assignment.
- Subjects will be informed that they they did not meet the protocol defined case definition of CAP caused by acute coccidioidomycosis infection.

-
- Refer subject to their health care provider with information as to treatment group assignment and disease status.
 - Those subjects who did not meet the protocol defined case definition of CAP caused by acute coccidioidomycosis infection will be dismissed from the study following data collection and referral.

Coccidioidomycosis Positive Subjects Who Received Placebo

- Subjects will be provided with all available coccidioidal serology results and their treatment group assignment.
- Subjects will be informed that they met the protocol defined case definition of CAP caused by acute coccidioidomycosis infection.
- Refer subject to their identified health care provider with for evaluation of need for initiation of treatment and clinical follow-up.

All coccidioidomycosis positive subjects will be followed through Day 180. These subjects will be provided the visual analogue scale and instructed on its measurement for assessment of extra-pulmonary symptom score for use during follow up phone visits (Visits 06 and 07) as well as with addressed/stamped envelope for returning to study team.

Coccidioidomycosis Positive and Negative Subjects Who Received Fluconazole

- Remind subject that contraceptives must be maintained until 30 days after the last dose of study medication.
- Refer to Section 5.2

7.3.4. Follow-up Visit 05 (Day 49) – Telephone follow-up for those subjects randomized to Fluconazole only:

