9.2.2. Serious Adverse Events

Serious Adverse Event (SAE): An adverse event or suspected adverse reaction is considered “serious” if, in the view of either the investigator or sponsor, it results in any of the following outcomes:

- Death
- A life-threatening adverse event*
- Inpatient hospitalization or prolongation of existing hospitalization
- A persistent or significant incapacity or substantial disruption of the ability to conduct normal life functions, or
- A congenital anomaly/birth defect
- Important medical events that may not result in death, be life-threatening, or require hospitalizations may be considered serious when, based upon appropriate medical judgment they may jeopardize the patient or subject and may require medical or surgical intervention to prevent one of the outcomes listed in this definition. Examples of such medical events include allergic bronchospasm requiring intensive treatment in an emergency room or at home, blood dyscrasias or convulsions that do not result in inpatient hospitalization, or the development of drug dependency or drug abuse

*Life-threatening adverse event. An adverse event is considered “life-threatening” if, in the view of either the site principal investigator or sponsor, its occurrence places the patient or subject at immediate risk of death. It does not include an adverse event that, had it occurred in a more severe form, might have caused death.

Death and life-threatening events are part of the efficacy endpoints of this trial and will not be reported or collected as SAEs unless they meet the criteria below.

Only the following events will be considered SAEs:

- Congenital anomalies or birth defect, OR
- Any condition that meets the regulatory definition of a SAE AND is unexpected (per PI) AND is suspected to be directly caused by the study drug (e.g., anaphylaxis, Stevens-Johnson syndrome, exfoliative dermatitis)

Protocol defined SAEs will be:

- Collected from the time of enrollment through visit Day 49
- Assessed for relationship to study product
- Recorded on the appropriate SAE form and eCRF
- Followed through resolution by a licensed study physician listed on the Form FDA 1572 as the site principal investigator or sub-investigator
- Reviewed and evaluated by DMID, the DSMB (periodic review), and the IRB

9.2.3. Procedures to be Followed in the Event of Abnormal Laboratory Test Values or Abnormal Clinical Findings

Study drug will be stopped for the individual subject if:

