9.4. Type and Duration of Follow-up of Subjects after Adverse Events

SAEs will be followed from the time of enrollment until completion of study even if this extends beyond the study-reporting period. For those subjects who are dismissed from study follow-up after study Day 43 (Visit 04), SAEs will be followed but new SAEs will not be collected. All subjects who received fluconazole will be followed through Day 49. Resolution of an SAE is defined as the return to pretreatment status or stabilization of the condition with the expectation that it will remain chronic.

Follow-up procedures, evaluations, and outcomes will be recorded on the appropriate data collection form.

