11.4.3. Safety Analysis Plan

Safety evaluations will be based on the incidence, severity, and type of clinically significant physical examination findings, clinically significant vital signs, and SAEs as defined in Section 9.2.2. Safety variables will be tabulated and presented for all subjects in the safety population, grouped by treatment group.

SAEs will be coded by the Medical Dictionary for Regulatory Activities (MedDRA) for preferred term and system organ class. The rate and exact 95% confidence intervals of related SAEs in aggregate, and by MedDRA categories, will be computed. The number of SAEs will be reported by a detailed listing showing the type, MedDRA coding, relevant dates (administration and adverse event), severity, relatedness, and outcome for each event.

Laboratory toxicities will be analyzed by taking the most severe response over the follow-up period, dichotomizing into a binary variable (none or mild versus moderate or severe) and using exact confidence intervals to summarize the event and toxicity rates. Tabular and graphical summaries of events will be presented for each solicited symptom, by type, severity (none, mild, moderate, severe), and time point post-administration.

Laboratory and vital sign data will also be presented as change from baseline. Variable transformations will be applied as appropriate. Shift tables may be produced for select laboratory parameters.

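### SAEs are actively sought to Day 49 on fluconazole, but no placebo subject has a scheduled SAE assessment after Day 43, and the by-arm SAE rates use no common window

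*Combined protocol and SAP*

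**What the plan says.** Two general statements name no arm. Section 4: "SAEs, as defined in the protocol, will be collected through Day 49". Section 9.2.2, on protocol-defined SAEs: "Collected from the time of enrollment through visit Day 49".

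The operating text is narrower:

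- Section 4, on the Day 49 contact: "All subjects who received fluconazole will be evaluated for safety follow-up at Day 49".
- Section 7.3.4, heading of Visit 05 (Day 49): "Telephone follow-up for those subjects randomized to Fluconazole only". The visit includes an SAE query. The footnote to Table 12 in Appendix A gives the same restriction.
- Section 9.4: "All subjects who received fluconazole will be followed through Day 49". For subjects dismissed after Day 43, "SAEs will be followed but new SAEs will not be collected".
- Section 4: at Day 43, subjects who do not meet the case definition and "who did not receive fluconazole will be dismissed from the study".
- Section 7.4.2: at an early termination after Visit 04, SAEs are assessed only in fluconazole recipients, and only before Day 49.

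On analysis, Section 11.4.3 says: "Safety variables will be tabulated and presented for all subjects in the safety population, grouped by treatment group". It adds rates of related SAEs with exact 95% confidence intervals. It gives no common cut-off, person-time denominator or on-treatment window.

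**The concern.** A by-arm rate is easy to interpret only if both arms are observed for the same period and in the same way. Here the fluconazole arm has an extra contact, about six days later, whose content includes asking about SAEs.

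That contact also falls after the blind is lifted. Section 5.3.2 keeps the blind only until the Day 43 assessments are complete. Under Section 9.2.2 an event other than a birth defect counts as an SAE only if it is serious, unexpected and suspected to be caused by study drug. In the extra days, an assessor who knows the assignment therefore decides whether an event enters the data at all.

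Section 9.2.1 rules out collecting non-serious adverse events, so the SAE table carries much of the clinical safety description.

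**Working it through.** The documents give no SAE rate, safety sample size or safety power, so there is no stated figure to reproduce. The check has three parts.

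**1. Who has a scheduled SAE assessment after Day 43**

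| Group | After Day 43 | Source |
|---|---|---|
| Fluconazole, any cocci status | Day 49 telephone SAE query | 7.3.4, 9.4, Table 12 |
| Placebo, cocci-negative | Dismissed at Day 43; new SAEs not collected | 4, 9.4 |
| Placebo, cocci-positive | Next contact Day 90, with no SAE assessment listed | 7.3.5, Table 12 |
| Early termination after Visit 04 | SAE assessment in fluconazole recipients only | 7.4.2 |

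For cocci-negative placebo subjects the stop is explicit. For cocci-positive placebo subjects it is inferred from the schedule. Both sit against the unrestricted Day 49 statements in Sections 4 and 9.2.2.

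**2. Length of the windows, counted from Day 1**

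- Nominal: (49 − 1)/(43 − 1) = 48/42 = 1.143, a gap of 6 days.
- The visit windows are Day 42 to 46 (Section 7.3.3) and Day 48 to 51 (Section 7.3.4).
- Smallest contrast: Day 48 against Day 46 is 47/45 = 1.04, a gap of 2 days.
- Largest contrast: Day 51 against Day 42 is 50/41 = 1.22, a gap of 9 days.
- If cocci-positive placebo subjects (20%, the planning value in Section 11.2.1) were in fact observed to Day 49, the mean placebo window would be 0.8 × 42 + 0.2 × 48 = 43.2 days, and the ratio 48/43.2 = 1.11.

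**3. Expected excess from the window alone**

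Assume 500 per arm (Table 1) and the same constant hazard in both arms. The Day 43 proportion with an SAE, p43, is also an assumption, varied over a range. Then p49 = 1 − (1 − p43)^(48/42), and the excess is 500 × (p49 − p43).

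| p43 (assumed) | p49 | Excess fluconazole subjects |
|---|---|---|
| 0.2% | 0.229% | 0.14 |
| 0.5% | 0.571% | 0.36 |
| 1% | 1.142% | 0.71 |
| 2% | 2.282% | 1.41 |
| 5% | 5.694% | 3.47 |
| 10% | 11.344% | 6.72 |

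For scale, at 1% the chance difference between arms has SD √(500 × 0.01 × 0.99 + 500 × 0.01142 × 0.98858) = √(4.95 + 5.64) ≈ 3.3 subjects. The shift of 0.71 is about 0.2 SD. With a common Day 43 cut-off the window ratio is 1.00, and this model gives no excess.

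**The case against.** **Late placebo events are not shut out.** A reader might infer that an SAE after Day 43 can be counted only on fluconazole. Section 9.3.1 does not support that. Sites must report a suspected-related SAE they learn of at any time after study completion, with no arm restriction. What is unequal is active solicitation. This point stands, with two limits: the section does not say that such reports enter the Section 11.4.3 tables, and an event in a subject known to have taken placebo is unlikely to be judged drug-caused.

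**Birth defects are largely unaffected.** Section 9.3.3 follows pregnancies to two months after birth in women who received either product. This stands.

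**The constant hazard fits poorly.** Section 4 gives 42 days of treatment, so the extra days come after the study course, and the SAE definition is limited to suspected drug-caused events. (Section 9.2.1 says relatedness does not decide reporting, but Section 9.2.2 is the specific rule.) This stands. The ratio of 1.14 measures observation time and does not forecast inflation in the SAE rate.

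**The scope is narrow.** It is tempting to say that the safety comparison as a whole is biased against fluconazole. The documents do not support that. Safety laboratory tests and scheduled vital signs end at Day 43 in both arms, as does mortality. The liver-function outcome rests on those tests. No between-arm SAE test is planned, and Section 9.2.1 says the trial is not powered to detect new safety signals.

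**Dates are already listed.** Section 11.4.3 requires event dates and relatedness for each SAE, so late events can be identified. This makes the remedy cheap, but the planned rates and intervals would still mix the two windows.

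**Conclusion.** The point holds in limited form. Followed as written, the plan gives by-arm SAE rates over unequal periods of active ascertainment, and the extra fluconazole days are unblinded. The sections on the collection period also contradict one another.

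The likely size is small: under one extra fluconazole subject in 500 if the Day 43 SAE proportion is 1% or less, and about 1.4 at 2%. These figures rest on an assumed rate and an equal constant hazard, neither of which comes from the documents. They do not include any effect of unblinded questioning and causality judgement, which would tend in the same direction but cannot be quantified here.

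The Day 49 call is not a defect in itself. The problem is pooling its events into a rate set beside placebo. This is a worthwhile correction and no threat to the trial's conclusions.

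**What to change.** In Section 11.4.3 and the separate statistical analysis plan, base the by-arm SAE rates and exact confidence intervals on events with onset up to the Day 43 visit, before the scheduled unblinding, in both arms. List later events separately and descriptively. State whether a rate is a proportion of subjects or is per person-time. A person-time denominator alone would adjust for the length of observation, but not for the unblinded ascertainment.

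Reconcile the unrestricted Day 49 statements in Sections 4 and 9.2.2 with Sections 7.3.4, 7.4.2 and 9.4 and the Table 12 footnote, so that the SAE collection period is stated once for each group. The documents do not settle which statement should prevail.

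The cost is about one sentence of analysis text and one textual reconciliation. The analysis change needs no new visit or data. The few late fluconazole events leave the by-arm rate but remain in the listing.

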4.1. Sub-studies

Any proposed sub-study that will be added at a future time will be approved by NIAID. All sub-studies will require, in addition, an independent protocol and IRB approval.

5. STUDY ENROLLMENT AND WITHDRAWAL

5.1. Subject Inclusion Criteria

Subjects eligible to participate in this study must meet all of the following inclusion criteria:

1. Aged ≥ 18 years and presenting for clinical care in coccidioidomycosis endemic areas.
2. Have a health care provider who has decided to treat community acquired pneumonia with antibacterials.
3. Be able to take and tolerate oral antibacterials/antifungals.
4. Able to understand the study and provide informed consent.
5. Willing and able to comply with study procedures and complete study visits.
6. Willing to allow access to medical records, and medical records are available to the study team.
7. The first dosage of study drug will be administered within 72 hours of presentation for care.
8. Able to swallow large pills.
9. Sexually active female subjects must be of non-childbearing potential* or, if of childbearing potential, must use a highly effective method of birth control**(captured on the appropriate data collection form)

*Non-childbearing potential is defined as being post-menopausal for at least 18 months or surgically sterile via bilateral oophorectomy or hysterectomy.

**Female subjects must avoid becoming pregnant by using one of the following acceptable methods of birth control for 30 days prior to study drug dosing and must be maintained for 30 days after last dose of study drug:

- a. Intrauterine contraceptive device; OR
 - b. Oral contraceptives; OR
 - c. Implanon®, Nexplanon®, DepoProvera®, contraceptive skin patch or NuvaRing®; OR
 - d. Tubal ligation; OR
 - e. Exclusively same-sex relationships
10. Non-pregnant female subjects of childbearing potential must have a negative pregnancy test within 24 hours prior to enrollment and at Visits 02 - 03.
 11. Subjects receiving any of the drugs reported to have manageable drug interactions with fluconazole (see section 6.6.2: Drug Interactions with Fluconazole) are allowed to be enrolled based on PI clinical judgment.

5.2. Subject Exclusion Criteria

Subjects eligible to participate in this study must not meet any of the following exclusion criteria:

1. Have recently received an experimental agent* or participating in or planning to participate in a study involving an experimental agent** while in the active drug administration phase of this study.
* defined as within 30 days prior to enrollment in this study
**(e.g., vaccine, drug, biologic device, blood product, or medication)
2. Present clinical diagnosis of hospital acquired pneumonia (HAP).
3. Documented microbiologically- or serologically-confirmed past infection with coccidioidomycosis.
4. Clinical diagnosis of coccidioidal infection that is of sufficient certainty as to exclude the need for antibacterial therapy.
5. Have a history of systemic antibacterial treatment for this current CAP care episode occurring greater than 4 weeks prior to enrollment.*
*Receipt of systemic antimicrobial therapy for indications other than respiratory tract infection is permitted.
6. Have a history of systemic antifungal treatment within the 4 weeks prior to enrollment.
*A single dose of fluconazole (ex. treatment of vulvovaginal candidiasis) is acceptable and should not exclude subject from study
7. Long term use* of high dose oral or parenteral glucocorticoids**; or high-dose inhaled steroids*** taken within the 4 weeks prior to enrollment.
*defined as > 8 weeks of daily use
**high dose defined as prednisone \geq 20 mg total daily dose, or equivalent dose of other glucocorticoids
***high dose defined as >800 mcg/day of beclomethasone dipropionate or equivalent
8. Have confirmed or suspected immunosuppression as a result of an underlying illness [other than well controlled HIV infection], primary immunodeficiency, or treatment, or induction/maintenance use of immunosuppressive agents*.
*including anti-neoplastic chemotherapy or cytotoxic radiation therapy for cancer, anti-TNF medications, or other immunomodulating agents
9. History of a solid organ or bone marrow transplant.
10. Have poorly controlled HIV-infection or HIV-infection treated with Lopinavir, Tipranavir, Etravirine or Didanosine. Poorly controlled HIV is defined as HIV RNA > 50 copies/mm³ (or greater than the lower limit of quantification [LLOQ] of the local HIV RNA assay if the LLOQ is >50) in the 6 months prior to current care

- episode regardless of whether patient is on antiretroviral therapy or CD4 < 250 cell/mm³.
11. Current diagnosis and/or treatment of active liver disease including abnormal baseline liver function tests as defined as: total bilirubin greater than or equal to 3.0mg/dL AND either AST greater than or equal to 135 IU/L OR ALT greater than or equal to 150 IU/L.
 12. On hemo or peritoneal dialysis or have a creatinine of ≥ 2.0 mg/dL or estimated CrCl ≤ 50 mL/min.
 13. History of hypokalemia defined as less than 3.5 mEq/L on more than one occasion during the 4 weeks prior to enrollment.
 14. History of cardiovascular disease with increased risk for torsades de pointes as defined as:
 - a. NYHA Heart Failure Criteria III or greater; OR
 - b. History of atrial or ventricular dysrhythmias; OR
 - c. History of structural heart disease (including previously repaired); OR
 - d. Personal or family history of congenital long QT syndrome.
 15. A marked baseline prolongation of the QT/QTc interval as defined as a QTc interval > 450 milliseconds (ms) for male subjects or > 470ms for female subjects with repeated demonstration*.

* Subjects without a history of prolonged QTc and an abnormal baseline QTc interval should undergo repeat ECG assessment within screening period prior to randomization (72 hours) to confirm prolongation. If the repeat ECG QTc is within normal limits and less than the parameters above, the subject may be considered for enrollment.
 16. Pregnant or lactating females.
 17. History of azole intolerance or allergy.
 18. Individuals for whom study participation would not be in their best interest, as determined by the clinical investigator.
 19. Are taking medications that are contraindicated with concurrent use of fluconazole (See Section 6.6.1: Contraindicated Medications).
 20. Positive point of care HIV test at Day 1 visit consistent with new HIV diagnosis.

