5.3.3.1. Discontinuation from Treatment

In addition, a subject will be discontinued from the active treatment and continue to be followed if the subject meets any of the following reasons:

- If any of the following criteria for liver-related adverse events are met and confirmed:
 - AST elevation of >5X ULN or greater than or equal to 225 IU/L or
 - ALT elevation of >5X ULN or greater than or equal to 250 IU/L or
 - Total bilirubin elevation >1.5X ULN or
 - Aminotransferase elevation of >3X ULN accompanied by total bilirubin elevation >1.5X ULN
- If any subject experiences any of the following:
 - QTc prolongation as defined by a corrected QT of > 500ms OR > 60ms above baseline measurement
 - Torsades de pointes (torsades, TdP)
 - Unexplained Syncope
 - Seizure in non-epileptic patients
- Medical disease or condition, or any new clinical findings that meet an exclusion criterion or for which continued participation, in the opinion of the site principal investigator or appropriate sub-investigator, would compromise the safety of the subject, would interfere with the subject's successful completion of the study, or would interfere with the evaluation of responses.
- A SAE as defined in the protocol. The subject will be followed until the resolution of the event.

-
- Pregnancy. The subject will be followed up to two months after delivery.
 - New information becomes available that makes further participation unsafe or no longer in the best interest of the subject.
 - Diagnosis of disseminated coccidioidomycosis.
 - Subsequent hospitalization for this CAP episode occurring greater than 72 hours after study randomization.
 - Worsening oxygenation: need for assisted ventilation including continuous positive airway pressure (CPAP), bilevel positive airway pressure (BIPAP), or mechanical ventilation.
 - Unable to adhere to scheduled study visits (e.g. relocation at a distance from the study center that precludes adherence)
 - Determined by a physician's discretion to require additional therapy not indicated in the protocol to ensure his/her health and well-being.

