8.2. Laboratory Evaluations

8.2.1. Clinical Laboratory Evaluations

Clinical screening laboratory parameters to be evaluated on Day 1 (or at pre-screening visit) to confirm study eligibility prior to receipt of the first study drug and will include a hepatic function panel (AST, ALT, Alkaline phosphatase, and total bilirubin), BUN, creatinine and HIV-1 POC testing. A urine or serum pregnancy test will be performed in women of child-bearing potential. To be eligible for participation in this trial the subject's clinical screening laboratory evaluations must be confirmed to meet the eligibility criteria as outlined in the Subject Eligibility Criteria.

- The hepatic panel (AST, ALT, Alkaline phosphatase, and total bilirubin), BUN, creatinine and POC HIV-1 testing will be performed by the local or site laboratory with same day resulting. A venous blood sample (approximately 10 mL) will be collected from each subject at the Day 1 or pre-screening visit. Safety labs completed as part of standard of care within the past 72 hours and that are available to the study team at the time of screening can serve as the screening activities and do not require repeating. (Laboratory screening tests are required to have the same normal range values as the primary study site).
- The urine or serum pregnancy test will be performed in women of child-bearing potential will be performed by the local or site laboratory with same day resulting. No additional sample will be needed if a serum test is desired.

Clinical safety laboratory parameters to be evaluated on Days 22, 29 and 43 include hepatic function panel (AST, ALT, Alkaline phosphatase, and total bilirubin), BUN, creatinine and pregnancy test (urine or serum) for women of child-bearing potential. These evaluations will be performed by the local or site laboratory with same day resulting. Venous blood samples (approximately 10 mL) will be collected from each subject on specified study days.

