- If any of the following criteria for liver-related adverse events are met and confirmed:
 - AST elevation of >5X ULN or greater than or equal to 225 IU/L or
 - ALT elevation of >5X ULN or greater than or equal to 250 IU/L or
 - Total bilirubin elevation >1.5X ULN or
 - Aminotransferase elevation of >3X ULN accompanied by total bilirubin elevation >1.5X ULN
- If any subject experiences any of the following:
 - QTc prolongation as defined by a corrected QT of > 500ms OR > 60ms above baseline measurement
 - Torsades de pointes (torsades, TdP)
 - Unexplained Syncope
 - Seizure in non-epileptic patients

The subject will be referred to an appropriate health care provider for treatment, and will be followed-up until stabilization or resolution.

The abnormal hepatic function testing will be documented on an appropriate eCRF.

Aggregate information regarding abnormalities of hepatic function testing will be presented to the DSMB in their regular meetings.

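### Exclusion 11 needs raised bilirubin and raised AST or ALT together, so no numeric entry rule excludes a Day 1 AST, ALT or paired value already at a liver stopping limit

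*Combined protocol and SAP*

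**What the plan says.** **Entry.** Exclusion 11 in Section 5.2 covers a current diagnosis or treatment of active liver disease and adds a laboratory definition: "total bilirubin greater than or equal to 3.0mg/dL AND either AST greater than or equal to 135 IU/L OR ALT" at or above 150 IU/L. This is the only numeric liver limit at entry.

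**Stopping.** Section 5.3.3.1 discontinues study drug "If any of the following criteria for liver-related adverse events are met and confirmed". Four alternatives follow: "AST elevation of >5X ULN or greater than or equal to 225 IU/L or" ALT above 5x ULN or at least 250 IU/L; total bilirubin above 1.5x ULN; and "Aminotransferase elevation of >3X ULN accompanied by total bilirubin elevation >1.5X ULN". Section 9.2.3 repeats the list. Neither section exempts a value that was already high at baseline.

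**Checks before dosing.** Section 8.2.1 says the subject's "clinical screening laboratory evaluations must be confirmed to meet the eligibility criteria as outlined in the Subject Eligibility Criteria". Section 7.2 requires the investigator to review the liver results and the eligibility criteria before randomisation. Exclusion 18 bars "Individuals for whom study participation would not be in their best interest, as determined by the clinical investigator".

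**Checks after dosing.** Section 8.2.1 schedules the next hepatic panels for Days 22, 29 and 43. Section 7.5 allows an unscheduled retest and gives raised liver enzymes as an example, but does not require one.

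**The concern.** Entry limits are normally at least as strict as the limits for stopping drug. Here the entry rule joins bilirubin to the aminotransferases, while the stopping rule separates them. A patient can start study drug with a value that, once confirmed, would on the plain terms of Section 5.3.3.1 take the patient off it.

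At stake is the safety of individual patients. Section 2.3.1 lists serious liver damage, including death, among the less common effects of fluconazole, and says most people enrolled will not have coccidioidomycosis. Section 9.1 says liver toxicity is reported particularly with co-morbidities and previous liver injury. Because the missing limit is left to judgement, similar patients may also be handled differently at different sites.

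**Working it through.** No sample-size or power figure is involved. The check compares the two rules.

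**1. Implied ULNs.** Section 5.3.3.1 pairs 5x ULN with 225 IU/L (AST) and 250 IU/L (ALT).
- AST: 225 / 5 = 45 IU/L. ALT: 250 / 5 = 50 IU/L.
- The Exclusion 11 cut-offs are then 135 / 45 = 3.0x and 150 / 50 = 3.0x ULN, but they count only when bilirubin is at least 3.0 mg/dL. Below that, no AST or ALT value excludes.

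**2. Paired limit.** The protocol gives no bilirubin ULN, so I write u for it and assume 1.0 to 1.5 mg/dL. The stopping limit is 1.5 x u and the entry limit is 3.0 mg/dL, so entry is looser whenever u < 3.0 / 1.5 = 2.0 mg/dL. A patient above 3x ULN on AST or ALT meets the paired stop but passes entry when bilirubin lies in these ranges:

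| Assumed u (mg/dL) | 1.5 x u | Gap in bilirubin (mg/dL) |
|---|---|---|
| 1.0 | 1.5 | above 1.5, below 3.0 |
| 1.2 | 1.8 | above 1.8, below 3.0 |
| 1.5 | 2.25 | above 2.25, below 3.0 |

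**3. Example Day 1 profiles** (no diagnosed liver disease; AST and ALT in IU/L, bilirubin in mg/dL):

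| AST | ALT | Bilirubin | Laboratory limb of Exclusion 11 | Stopping limits met |
|---|---|---|---|---|
| 40 | 260 | 0.8 | passes (0.8 < 3.0) | ALT (260 >= 250) |
| 300 | 40 | 0.8 | passes (0.8 < 3.0) | AST (300 >= 225) |
| 220 | 240 | 2.9 | passes (2.9 < 3.0) | paired (220 > 135, 240 > 150, with 2.9 > 1.5 x u) |
| 300 | 400 | 2.9 | passes (2.9 < 3.0) | AST, ALT and paired |
| 135 | 40 | 3.0 | excluded | – |

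The first two rows use the protocol's own IU/L limits and need no ULN. The paired results in rows three and four use the implied ULNs and hold for any u below 2.9 / 1.5 = 1.93 mg/dL.

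**4. Alternative parsing.** If Exclusion 11 is read as (bilirubin and AST) or ALT, the ALT examples are excluded. AST 400 with ALT 40 and bilirubin 0.8 still passes.

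**5. Exposure before the next scheduled panel.** The first dose is on Day 1 and the Day 22 visit window runs from Day 20 to Day 23 (Section 7.3.1). Counting both ends, that is 20 to 23 daily doses if nobody excludes or retests. With 1:1 randomisation, about half of such patients would receive fluconazole.

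**6. Comparison with QTc.** Exclusion 15 uses 450 ms (men) and 470 ms (women), below the 500 ms stop in Section 5.3.3.1. Patients with an abnormal first tracing and no history of prolonged QTc "should undergo repeat ECG assessment within screening period prior to randomization (72 hours) to confirm prolongation". The liver has no equivalent.

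**The case against.** **The stopping list may concern only new elevations.** It is headed as liver-related adverse events, and Section 9.2.1 ties an adverse event to product having been given. The halting rule in Section 9.5 speaks of subjects developing elevations, and Exploratory Outcome 7 applies the same limits to a rise from the Day 1 value. A reader might infer from the entry and stopping rules that the protocol certainly removes these patients. The documents do not support that much: the wording is open. The limits are nevertheless absolute, and Section 5.3.3.1 makes no baseline exemption. On the narrower reading, no numeric rule covers a high baseline outside the combined exclusion, so the gap remains in a different form.

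**Several safeguards exist.** The diagnosis limb of Exclusion 11, the Day 1 liver history and examination, the laboratory review before randomisation, Exclusion 18, discontinuation on the investigator's safety opinion, and unscheduled retesting could each catch the patient. A careful investigator would probably notice AST 300 with ALT 400. This stands as a reason to treat 20 to 23 doses as a worst case. It does not close the gap, because none of these safeguards has a liver threshold.

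**Entry and stopping rules need not coincide.** That is true, and no section says they were meant to. A reader might infer that the conjunction is a drafting slip, but nothing in the documents shows it. Equally, no reason is given for admitting patients at a stopping level.

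**Isolated bilirubin.** It is tempting to require exclusion for any bilirubin above 1.5x ULN, since that alone is a stopping limit. This is more debatable as an entry limit: at the assumed ULNs it would exclude from just above 1.5 to 2.25 mg/dL, well under the sponsor's 3.0 mg/dL.

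**Conclusion.** The point holds for AST alone, ALT alone and the aminotransferase–bilirubin pair. For a patient with no diagnosed liver disease, a Day 1 value at one of those stopping limits is not excluded by any number in the protocol unless bilirubin is also at least 3.0 mg/dL. Whether the patient is excluded or retested early depends on the investigator.

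The single-enzyme result rests only on the stated IU/L limits. The paired result also assumes a bilirubin ULN below 2.0 mg/dL. That such a patient must be stopped once the value is confirmed follows from the plain terms of Section 5.3.3.1, subject to the wording noted above.

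The documents give no basis for estimating how many patients are affected. A reader might infer bias in the efficacy comparison; nothing here supports that, and none is claimed. This is a safety gap in the entry criteria that is worth closing.

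**What to change.** Keep the existing combined criterion and add to Exclusion 11: a Day 1 or pre-screening value meeting the AST, the ALT or the paired aminotransferase–bilirubin stopping limit in Section 5.3.3.1 also excludes, unless a repeat before randomisation and within the 72-hour window is below the limit. This follows the approach of Exclusion 15. The sponsor should decide separately whether isolated bilirubin above 1.5x ULN also excludes.

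Moderate rises would stay eligible when the paired limit is not met. At the implied ULNs, AST 224 is 224 / 45 = 4.98x and ALT 249 is 249 / 50 = 4.98x, both under 5x. A site with a lower local ULN would apply its own 5x limit.

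The cost is protocol wording plus some additional screen failures or repeat panels, a number the documents do not give. The panel is already reviewed before randomisation with same-day results (Sections 7.2 and 8.2.1). A repeat may not always fit: standard-of-care results can be up to 72 hours old when used, and Inclusion 7 requires the first dose within 72 hours of presentation. A patient who cannot be retested in time would be excluded.
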